5.1.2. Baseline Definitions

For all endpoints, the baseline value will be the latest pre-treatment assessment visit with a non-missing value. i.e., If an assessment has been made both at screening visit (Visit 1) and Week 0 infusion 1 visit (Visit 2, Week 0), the value from the Week 0 visit is used as the baseline value. If the value measured at the Week 0 visit is missing and the assessment also has been made at screening, then the screening value is used as the baseline value.

Unless otherwise stated, if baseline data is missing no derivation will be performed and baseline will be set to missing.

5.2. **Primary Endpoint(s) Analyses**

The primary objective of this study is to compare HB-adMSCs to Placebo on change in Visual Analog Scale of Neurological Symptoms scores. Efficacy analysis set will be used for this analysis. The details of the planned displays are in programming specification document.

5.2.1. **Definition of endpoint(s)**

Objectives	Endpoints
Primary Objective	Primary Endpoint
To investigate the efficacy of intravenous infusions of HB-adMSCs (allogeneic) vs. Placebo in patients with Chronic Post-COVID-19 Syndrome as determined by improvements in individual symptom scores of Visual Analog Scale of Neurological Symptoms. (Time frame: Baseline to Week 26).	Changes in the Visual Analog Scale of Neurological Symptoms. VAS are psychometric measuring tools intended to document the characteristics of disease-related symptom severity in individuals. The neurological symptoms included in this scale are (1) extreme fatigue (2) brain fog, (3) headache (4) sleep disturbances (5) loss of taste/smell.

5.2.2. Main analytical approach

Endpoint/Variables

• Change from baseline in Visual Analog Scale of Neurological Symptoms score following treatment with HB-adMSCs or Placebo at Week 26.

Primary analysis

ANCOVA Model Specification

- To compare the HB-adMSCs to Placebo on Change from baseline to Week 26, a standard Analysis of Covariance (ANCOVA) model will be fitted
- Terms fitted in the mixed effect model will include:

- Primary endpoint efficacy measurements available at Week 26 will be response variable in a linear mixed model using a variance-covariance residual matrix.
- The model will include:
 - Fixed factors: treatment
 - Covariate: baseline
 - Stratification: pre-existing condition prior to COVID-19 (Y/N), average VAS score of Neurological Symptoms (<5cm/>=5cm) and age group (<43/>=43)

Model Checking and Diagnostics

For the ANCOVA Model assumptions will be checked, and appropriate adjustments may be applied based on the data.

Distribution assumptions underlying the model used for analysis will be examined by obtaining a normal probability plot of the residual and a plot of the residuals versus the fitted values (i.e., checking the normality assumption and constant variance assumption of the model respectively) to gain confidence that the model assumptions are reasonable.

Non-parametric analyses, Mann-Whitney U (or Wilcoxon Rank-Sum) Test will be conducted if the normality assumptions does not hold.

Results presentation

Presentation of results from a statistical analysis model will include the estimated mean treatment effects (Least Square Means (LSMeans)) and estimated mean treatment differences will be presented together with two-sided 95% confidence intervals standard error for mean difference and p-value.

Endpoint/Variables

Change from baseline in Visual Analog Scale of Neurological Symptoms score following treatment with HB-adMSCs or Placebo at Week 2, Week 6, Week 10, Week 14, Week 20 and Week 26.

Secondary analysis

Repeated Measures Model Specification

- To compare the HB-adMSCs to Placebo on Change from baseline, a Repeated measures analysis (RMA) model will be fitted
- Terms fitted in the mixed effect model will include:
 - All primary endpoint efficacy measurements available at post-baseline at scheduled measurements will be response variable in a linear mixed model using an unstructured residual covariance matrix.
- The model will include:
 - Fixed factors: treatment and visit
 - Covariate: baseline
 - Stratification: pre-existing condition to COVID-19 (Y/N), average VAS score of Neurological Symptoms (<5cm/>=5cm), and age group (<43/>=43)
- Furthermore, the model will include:

- Interaction terms between treatment and visit
- And Interaction terms between baseline and visit
- Subject will be included as a random factor

Model Checking and Diagnostics

For the Repeated Measures Analysis (RMA) Model assumptions will be checked, and appropriate adjustments may be applied based on the data.

Distribution assumptions underlying the model used for analysis will be examined by obtaining a normal probability plot of the residual and a plot of the residuals versus the fitted values (i.e., checking the normality assumption and constant variance assumption of the model respectively) to gain confidence that the model assumptions are reasonable.

Non-parametric analyses, Mann-Whitney U (or Wilcoxon Rank-Sum) Test will be conducted if the normality assumptions does not hold.

Results presentation

Presentation of results from a statistical analysis model will include the estimated mean treatment effects (Least Square Means (LSMeans)) and estimated mean treatment differences will be presented together with two-sided 95% confidence intervals standard error for mean difference and p-value.

Additional analysis

Summary analysis method

To compare difference between baseline to Week 2, Week 6, Week 10, Week 14, Week 20 and Week 26, a paired t-test will be used for primary endpoint change from baseline VAS to check the statistical significance. Clinical significance will be determined using the established (published) MCID value for the VAS change from baseline. The available MCID value for Change from baseline VAS measure is provided in the Table 1 which will be used as a threshold to evaluate/identify clinically relevant changes.

To further evaluate if the improvements are clinically relevant, effect size of the treatment difference at Week 2, Week 6, Week 10, Week 14, Week 20 and Week 26 will also be calculated for the efficacy endpoint VAS score using cohen's d calculation. Cohen's d is a standardized measure of effect size (ES) that provides information on the amount of change in the outcome meaure relative to the variation within the measure. Cohen's d is calculated as the difference between the HB-adMSCs mean score and Placebo mean scores divided by the standard deviations of the scores. An absolute effect size of <0.2 will be considered trivial, ≥ 0.2 as small, ≥ 0.5 as medium and >0.8 as large ^[1].

Cohen's d = $\frac{M1-M2}{(sd1+sd2)/2}$, where M1 and M2 are the Mean scores for HB-adMSCs and Placebo respectively, and SD1 and SD2 are the corresponding standard deviations.

Table 1 Established MCID values for the outcome measures.

Outcome measure	MCID
VAS (Pain)	-1.9 [2]

MCID will be calculated as the mean change from baseline, to compare the result with the reference values established in the literature (provided in Table 1) for ΔVAS Score. Clinically important improvements for VAS score will be defined as mean change from baseline \geq established (published) MCID.

Results presentation

Secondary endpoints will be summarized using n, mean, confidence interval of mean, SD, median, minimum and maximum. And p-value for paired comparison will be displayed for all post-baseline visits.

Normality checking

Distribution assumptions used for the statistical analysis will be examined by obtaining a normal plot and Shapiro-Wilk Test.

Non-parametric analyses, Wilcoxon signed-rank test will be conducted if the normality assumption does not hold.

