A repeated measure mixed model will be used to assess within-subject changes from baseline. Correction for multiple comparisons will be employed for post-hoc comparisons. Chronic Post COVID-19 Syndrome's assessments (VAS, FAS, PHQ-9, and SF-36) at infusion 1 (before treatment) will be utilized as a baseline.

Data Handling

Case Report Forms (CRF)

As used in this protocol, the term CRF should be understood to refer to either a paper form or an electronic data record, or both. Reports received by the site, or the central laboratory should be printed, retained as source documentation, and signed by the principal investigator, indicating which values are considered clinically significant and reported as AEs if applicable.

The completion, review, and approval of all CRFs and the completeness and authenticity of all clinical and laboratory data entered on these CRFs are always the Principal Investigator's responsibility. The signature of the Principal Investigator will be required to attest that the information contained on the CRFs is accurate.

Changes in the Conduct of the Clinical Trial

Protocol Amendments

Any change to the protocol will need to have a protocol amendment submitted to the IND, and FDA and IRB must agree before proceeding.

Premature Clinical Trial Termination

Both the Study Investigator and Sponsor have the right to terminate the clinical trial at any time. Should this become necessary, the procedures will be agreed upon after consultation between the two parties. In terminating the clinical trial, the Sponsor and the Study Investigator will ensure that adequate consideration is given to protect the best interests of the study participants. Regulatory authorities and IRB will be informed.

In addition, the Sponsor reserves the right to terminate the participation of any clinical trial site. Conditions that may warrant termination include, but are not limited to:

- Insufficient adherence to protocol requirements
- Failure to enter patients at an acceptable rate
-

Reporting and Publication

Neither the complete nor any part of the study results carried out under this protocol nor any of the information provided by the sponsor to perform the study will be published or passed on to any third party without the consent of the study sponsor.

Any investigator involved with this study is obligated to provide the sponsor with complete test results and all data derived from the study.

Archiving

Investigator File

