5.1.1. General Methodology

Unless otherwise stated, all hypotheses will be tested at a 2-sided significance level of 0.05 and 95% confidence interval. All continuous measurements will be summarised descriptively at each visit by treatment using observed data.

Summary of continuous variables will be presented using N, Mean, 95% confidence interval of mean, Standard Error of mean (SE), Standard Deviation (SD), Median and Range (Minimum and Maximum). The categorical variables will be presented using number and percentage based on N.

For measurements over time mean values will be plotted to explore the trajectory over time. Observed data will be used as the basis for plotting data along with bars as +/- SE, not otherwise specified.

As a primary analysis, a standard Analysis of Covariance (ANCOVA) will be applied for primary and secondary endpoint to test the significance of the effects of the treatment at Week 26. The model includes treatment as fixed factor and the corresponding baseline value as a covariate.

A parametric Repeated Measures Analysis (RMA) Model will be applied as a secondary analysis to test the significance of the effects of the treatment at Week 2, Week 6, Week 10, Week 14, Week 20 and Week 26 including baseline as covariate.

Presentation of results from a statistical analysis model will include the estimated mean treatment effects (Least Square Means (LSMeans)). For all endpoints analysed statistically, estimated mean treatment differences will be presented together with two-sided 95% confidence intervals and p-values,

HB-adMSCs - Placebo

Pairwise t-test will be performed on the efficacy endpoints to test the difference between baseline and week 26 (EOS) as secondary analysis. Data for all the efficacy outcomes will be checked for normality (Shapiro-Wilk Test).

When there is a larger deviation of data distribution from normality, appropriate nonparametric test will be used.

Study population analyses including analyses of subject disposition, demographic and baseline characteristics, medical history, prior and concomitant medications.

Disposition summary includes, subject screened, randomized and disposition at end of study – Week 26 along with reasons for withdrawals. Subjects in different analysis populations also will be presented.

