5.3. Secondary Endpoint(s) Analyses

5.3.1. Efficacy Endpoints / Variables

- Changes in Subject's energy and stamina as evidenced on the Fatigue Assessment form.
- Changes in Visual Analog Scale of non -Neurological Symptoms. The symptoms included in this scale are (1) dyspnea a rest and with activity, (2) cough, (3) body aches, and (4) joint pain.
- Changes in Subject's quality of life as evidenced by the Short Form 36 Health Survey Questionnaire.
- Changes in Subject's level of depression as evidenced by the PHQ 9 scale.

Primary analysis

Primary analysis of Repeated Measures Analysis (RMA) Model will be performed for above secondary efficacy endpoints above as given in the Section 5.2.2.

Secondary analysis

Secondary analysis of ANCOVA model will be perfored to test the significance of treatment difference for secondary efficacy endpoints above as given in the Section 5.2.2.

Additional analysis

Additional analysis of paired comparison will be performed using paired t-test to check for statistical significance will be performed for above secondary efficacy endpoints above as given in the Section 5.2.2.

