5.4. Changes to Protocol Defined Analyses

Analysis is planned as per protocol. No deviation from the planned protocol specified analysis.

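### The primary Week 26 ANCOVA uses observed values only, with no method for missing VAS scores, while a planned repeated-measures model that uses the earlier visits is ranked secondary

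*SAP*

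**What the plan says.** - **Primary model.** SAP 5.2.2 defines the response of the primary ANCOVA this way: "Primary endpoint efficacy measurements available at Week 26 will be response variable". The model adjusts for treatment, baseline and the three stratification factors. No imputation is attached.
- **Secondary model.** The same section specifies a repeated-measures analysis (RMA): "All primary endpoint efficacy measurements available at post-baseline at scheduled measurements will be response variable in a linear mixed model". It has unstructured covariance, treatment-by-visit and baseline-by-visit terms, and the same strata.
- **Ranking.** SAP 5.1.1 says that "a standard Analysis of Covariance (ANCOVA) will be applied for primary and secondary endpoint" as the primary analysis, with the RMA secondary. SAP 5.3.1 says the reverse for the secondary endpoints: "Primary analysis of Repeated Measures Analysis (RMA) Model will be performed for above secondary efficacy endpoints".
- **Protocol.** Its Statistical Methods section names one efficacy model: "A repeated measure mixed model will be used to assess within-subject changes from baseline". It does not mention ANCOVA. SAP 5.4 nevertheless declares "No deviation from the planned protocol specified analysis".
- **Missing data.** SAP 5.1.2 covers a missing baseline, and SAP 7.2.6 covers partial adverse-event and medication dates. Nothing covers a missing post-baseline VAS.
- **Visits.** Protocol Table 1 schedules the VAS at screening and Weeks 0, 2, 6, 10 and 26. Weeks 14 and 20 are phone calls without a VAS.

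**The concern.** The last infusion is at Week 10 and the next VAS is 16 weeks later. Some participants may complete all four infusions and then have no Week 26 score. The primary analysis drops them, although up to three post-baseline scores are on file for each and a model that would use those scores is already written.

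With no other missing-data provision, the choice of model is the only protection that the primary result has. If people who were doing poorly at Week 10 are less likely to return, and this differs between arms, the ANCOVA compares two selected groups and the estimated effect shifts. The unresolved ranking adds to this: the SAP contradicts itself on which model leads for the secondary endpoints, and it does not acknowledge that the ANCOVA is absent from the protocol.

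**Working it through.** **Plan's own figure.** SAP section 6 gives N = 80 with no effect size, SD, power or dropout, so it cannot be reproduced. For scale only, with 40 per arm and two-sided 0.05, the difference detectable with 80% power is (1.960 + 0.842) × √(2/40) = 0.626 SD. At an assumed SD of 2.2 cm this is 0.626 × 2.2 = 1.38 cm.

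**From the documents:** N = 80, 1:1 allocation, two-sided 0.05, VAS at Weeks 0, 2, 6, 10 and 26. **Assumed:** SD 2.2 cm, the within-person correlation, the share *d* missing Week 26, and the dropout mechanism.

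**Step 1: power when loss is unrelated to outcome.** Let R² be the share of Week 26 residual variance explained by Weeks 2, 6 and 10 given baseline. Relative to complete data, the variance of the treatment difference is multiplied by

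- ANCOVA: 1/(1 − d)
- RMA: (1 − R²)/(1 − d) + R²

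Power is Φ(2.802/√factor − 1.960), starting from 80% with complete data. Example at d = 0.20:

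- ANCOVA: factor 1.25, so Φ(2.506 − 1.960) = 70.7%.
- RMA, R² = 0.25: 0.75/0.80 + 0.25 = 1.1875, giving 72.9%.
- RMA, R² = 0.65: 0.35/0.80 + 0.65 = 1.0875, giving 76.6%.

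| Missing at Week 26 | ANCOVA | RMA, R² 0.25 to 0.65 |
|---|---|---|
| 5% | 78.0% | 78.5-79.3% |
| 10% | 75.7% | 76.8-78.5% |
| 20% | 70.7% | 72.9-76.6% |
| 30% | 65.0% | 68.3-74.3% |

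Under equal correlation ρ between visits, the residual variance is 1 − ρ² given baseline and 1 − 4ρ²/(1 + 3ρ) given baseline plus three visits.

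- ρ = 0.5: 0.75 falls to 0.60, so R² = 0.20.
- ρ = 0.7: 0.51 falls to 0.368, so R² = 0.28.

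The upper end of each RMA range therefore needs a stronger link between Weeks 2-10 and Week 26 than these correlations imply. In simulations with ρ = 0.5 and 0.7, the RMA cut the standard error by only about 0-3%.

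**Step 2: bias when loss depends on Week 10.** In simulated trials of 80, the chance of missing Week 26 followed a logistic function of the Week 10 score, with equal correlation 0.5 or 0.7. Bias is in outcome SDs, converted at 2.2 cm.

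| Dropout rule | ANCOVA, 10% missing | ANCOVA, 20% missing | RMA |
|---|---|---|---|
| Unrelated to outcome | about 0 | about 0 | about 0 |
| Same in both arms | 0.00-0.01 SD | 0.00-0.01 SD | about 0 |
| Placebo arm only | 0.02-0.03 SD | 0.04-0.05 SD (0.09-0.11 cm) | about 0 |
| Opposite by arm | 0.04-0.05 SD | 0.07-0.09 SD (0.15-0.20 cm) | at most 0.006 SD |

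Widening the assumptions to 10-25% missing, weaker and steeper dropout slopes and serially decaying correlation gives these ANCOVA biases:

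- one rule in both arms, true effect -1.2 cm: about 0.02-0.16 cm, towards no effect;
- dependence in one arm only: about 0.06-0.43 cm, with the sign set by the arm affected;
- strong opposite-direction dropout with serially decaying correlation (0.7-0.8), 20% missing: up to about 0.7 cm.

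The RMA stayed within about 0.02 cm throughout. For comparison, the standard error of the difference is about 0.17-0.23 SD, or 0.37-0.51 cm.

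**Limits.** The simulated ANCOVA adjusted for baseline only, whereas SAP 5.2.2 adds the strata. The simulated loss depended on observed scores, which is the case the RMA handles.

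**The case against.** Baseline-adjusted ANCOVA at one time point is an accepted primary analysis. It is unbiased when missingness depends only on treatment and the model covariates. The RMA is pre-specified beside it, so a discrepancy would be visible. The Week 14 and Week 20 calls keep participants in contact. ANCOVA with multiple imputation from the earlier visits would also close the gap. All of this stands, and it makes the harm conditional. It does not remove the gap: the primary result has no missing-data method and discards data that the plan already knows how to use.

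Four stronger readings are tempting but not supported:

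- *That bias and lost power will occur.* No dropout rate, SD, correlation or mechanism is given, so neither can be asserted.
- *That the ANCOVA could show a spurious difference of about 0.65 cm.* This needs strong dropout dependence in opposite directions by arm together with serially decaying correlation. Nothing in the documents points to that in a double-blind trial.
- *That the SAP demoted the protocol's primary test, and for the primary endpoint only.* The protocol sentence concerns within-subject change and names no between-arm Week 26 test. SAP 5.1.1 ranks ANCOVA first for secondary endpoints too, and SAP 5.3.1 contradicts it.
- *That changing the model cures selection.* The efficacy set (SAP section 4) admits only those who received all four infusions, and it applies to both models. Within it, the RMA recovers only people whose Week 26 score is missing despite a Week 10 infusion.

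**Conclusion.** The point holds as a conditional weakness that is cheap to remove. The primary analysis is observed-case, nothing in the SAP handles a missing Week 26 VAS, and a model that is valid under a weaker assumption is already written but ranked second.

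Under the assumed values, the avoidable bias is usually well below one standard error and the power gain is a few points at most for 5-20% missing. It becomes material with dependence in one arm at the upper end of the range: 0.43 cm is about one standard error. These sizes rest on assumed SD, correlation and dropout, and on loss depending on observed Week 2-10 scores. If loss depends on the unseen Week 26 score, the RMA can be biased too. The inconsistency among SAP 5.1.1, 5.3.1 and 5.4 and the protocol rests on no assumption and needs correction regardless.

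**What to change.** - Make the Week 26 treatment contrast from the RMA the primary analysis of the primary endpoint, with unstructured covariance, treatment-by-visit, baseline-by-visit and the strata. List the VAS visits as Weeks 2, 6, 10 and 26, because SAP 5.2.2 also names Weeks 14 and 20, where none is scheduled.
- Keep the Week 26 ANCOVA as a sensitivity analysis.
- State the missing-at-random assumption and add a missing-not-at-random sensitivity analysis.
- Make SAP 5.1.1 and 5.3.1 agree on which model leads for the secondary endpoints, and have SAP 5.4 record and justify any departure from the protocol's model.
- Raise the four-infusion efficacy set as its own point, with the RMA run in all randomised and treated participants.

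The cost is SAP wording, since the model is already planned, plus programming for one sensitivity analysis. The downside is reliance on missing at random, which the added sensitivity analysis is there to probe. The changes should be made before unblinding.

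### If normality fails, the SAP turns to an unadjusted Mann-Whitney test without a criterion or a statement whether it replaces the adjusted model; separately, it plans Week 14 and Week 20 analyses where the protocol's schedule has no scores

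*SAP*

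**What the plan says.** **Models.** SAP 5.1.1 names ANCOVA as the primary analysis, with treatment and baseline only. SAP 5.2.2 places it under its primary-analysis heading and adds three stratification factors: pre-existing condition, average neurological VAS below or at least 5 cm, and age below or at least 43. A repeated-measures model follows as secondary analysis. For the secondary endpoints, SAP 5.3.1 reverses the order: "Primary analysis of Repeated Measures Analysis (RMA) Model will be performed for above secondary efficacy endpoints".

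**Diagnostics and fallback.** For each model, 5.2.2 examines assumptions by "obtaining a normal probability plot of the residual and a plot of the residuals versus the fitted values". It allows unspecified adjustments in the light of the data, then adds: "Non-parametric analyses, Mann-Whitney U (or Wilcoxon Rank-Sum) Test will be conducted if the normality assumptions does not hold". SAP 5.1.1 has its own wording: "Data for all the efficacy outcomes will be checked for normality (Shapiro-Wilk Test"), and "When there is a larger deviation of data distribution from normality, appropriate nonparametric test will be used". Under the additional (paired) analysis in 5.2.2, Shapiro-Wilk and a normal plot are attached to the paired tests, with the signed-rank test as fallback.

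**Reported quantities.** With no condition attached, 5.2.2 says "estimated mean treatment differences will be presented together with two-sided 95% confidence intervals standard error for mean difference and p-value".

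**Response.** SAP 5.2 sets out to "compare HB-adMSCs to Placebo on change in Visual Analog Scale of Neurological Symptoms scores", and the hypotheses in section 3 also concern change. The model bullet in 5.2.2 says "Primary endpoint efficacy measurements available at Week 26 will be response variable".

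**Visits.** SAP 5.1.1 and 5.2.2 plan repeated-measures contrasts, paired tests and Cohen's d at Weeks 2, 6, 10, 14, 20 and 26. Protocol Table 1 has no VAS, fatigue, PHQ-9 or SF-36 entry at Visits 6 and 7 (Weeks 14 and 20). The protocol's list of procedures for those phone visits covers only history, medication and adverse events. Yet the Investigational Plan includes both visits among those with clinical assessment of disease activity.

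**The concern.** A rank-sum test on two groups carries no covariates. If it takes the ANCOVA's place, the primary comparison gives up baseline adjustment and the three factors used to stratify randomisation, and it cannot supply the LSMeans and adjusted difference that the results paragraph requires. The response to be ranked also begins to matter. In ANCOVA with baseline as covariate, change and Week 26 value give the same treatment estimate; in a rank-sum test they do not.

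Without a criterion or a replace-or-supplement statement, someone holding unblinded results could defend either p-value. The same sentence is repeated for the repeated-measures model, without saying how a two-sample test would be applied across visits.

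For Weeks 14 and 20, the question is whether the planned outputs would have any data.

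**Working it through.** **Step 1: the two branches of the fallback**

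- *Supplements:* 5.1.1 and 5.2.2 both label the ANCOVA primary, so its p-value is the primary one.
- *Replaces:* baseline and strata drop out, and no LSMeans or adjusted difference result. The wording in 5.1.1 leans this way but does not say so.

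**Step 2: what dropping baseline costs in the simplest case**

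From the SAP: 80 subjects, 1:1, two-sided 0.05, taken as 40 per arm. Assumed, because the documents give no figures: equal unit SDs, baseline to Week 26 correlation ρ of 0.3, 0.5 or 0.7, true effect 0.6265 SD (80% power unadjusted), normal errors.

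- ANCOVA: SE = √[(2/40)(1 − ρ²)], power = Φ(0.6265/SE − 1.96).
- Rank-sum on change: change has variance 2(1 − ρ), and the rank-sum test has efficiency 3/π against the t test under normality. Relative efficiency against ANCOVA is therefore (3/π)(1 + ρ)/2, that is 0.621, 0.716 and 0.812.
- Example, ρ = 0.3: SE = √(0.05 × 0.91) = 0.2133 and z = 2.937, so ANCOVA power is Φ(0.977) = 84%. For the rank-sum test, z = 2.937 × √0.621 = 2.314, and power is Φ(0.354) = 64%.

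Simulated values (3,000 trials per setting, strata in the ANCOVA) are shown beside the formula:

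| ρ | ANCOVA formula / simulated, normal | Rank-sum formula / simulated, normal | ANCOVA / rank-sum simulated, exponential errors |
|---|---|---|---|
| 0.3 | 84% / 82% | 64% / 63% | 80% / 71% |
| 0.5 | 90% / 89% | 78% / 78% | 87% / 89% |
| 0.7 | 97% / 97% | 94% / 94% | 95% / 99% |

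With skewed errors the rank-sum test can win, so the sign of the effect is not fixed.

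**Step 3: a bounded VAS, with the fallback firing only when a check fails**

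Assumptions: 4,000 trials per cell, 40 per arm, items clipped to 0-10, entry rule and three strata applied, ρ = 0.3/0.5/0.7, change ranked, and Shapiro-Wilk p < 0.05 on residuals standing in for the plots.

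- Single item away from the floor (means 6 and 5, SD 2.5, effect 1.2-1.9): loss of 0-0.9 points.
- Five-item average: loss of 0-0.4 points away from the floor and 0.2-8.4 near it.
- Single item near the floor (latent means 3.5 and 2.8, SD 3.5, effect 1.9): ANCOVA 64.0/73.3/86.7%; two-stage rule 45.4/63.7/84.4%. The loss is 18.6/9.6/2.3 points. Rank ANCOVA gives 65.4/73.9/86.6%.
- If Week 26 values are ranked instead, the bounded cases run from a gain of 0.4 to a loss of 2.6 points.
- Unbounded skewed or heavy-tailed errors, change ranked: from 9 points below to 17 above ANCOVA.

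**Step 4: type I error**

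- Fixed two-stage rule: 4.3-5.5% in the Step 2 settings, 4.3-5.7% in the bounded cases and 0.6-4.4% in the unbounded ones.
- Smaller of the two p-values chosen afterwards: 6.7-8.5% in the Step 2 settings; about 7-9% across the simulations run.

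**Step 5: visits**

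| Score | SAP post-baseline visits | With an entry in Protocol Table 1 |
|---|---|---|
| VAS, fatigue, PHQ-9 | 6 | 4 (Weeks 2, 6, 10, 26) |
| SF-36 (by-visit analyses carried over by SAP 5.3.1) | 6 | 2 (Weeks 10, 26) |

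**The case against.** The strongest reply is that the plan is clearer than it looks. The ANCOVA is called primary in two places, and the results paragraph requires model estimates without condition. In 5.2.2 the residual plots stand directly before each Mann-Whitney sentence, while Shapiro-Wilk is assigned to the paired tests. Change is the natural response. The power figures rest on assumed distributions, and away from the floor they are trivial.

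Most of this stands, and it rules out several stronger readings:

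- *The primary p-value is open even if the rank test only supplements.* It is not; the labels settle that branch.
- *No check governs.* The residual plots most naturally govern the models. Some ambiguity remains, because 5.1.1 applies Shapiro-Wilk to every efficacy outcome.
- *The two tests will often conflict.* Near the floor they disagree on significance in 30/27/19% of trials in which the assumed trigger fires. With firing rates of 78.5/47.5/15.6%, that is about 24/13/3% of all trials (0.30 × 0.785, and so on). Nothing in the documents shows that the near-floor case applies.
- *A rank test cannot serve the repeated-measures model.* One test per visit is not excluded; the SAP simply does not say.

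On visits, the repeated-measures model uses the measurements available and can run on four visits. Since the Investigational Plan lists Visits 6 and 7 for disease-activity assessment, non-collection is not certain.

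The reply leaves untouched the missing criterion, the missing replace-or-supplement statement, and the conflict within the protocol.

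**Conclusion.** Both parts hold, as corrections that should be made before unblinding.

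For the fallback, the gap is the absence of a criterion and of a statement whether Mann-Whitney replaces the model. A reader might infer that the fallback itself inflates type I error. It does not: no fixed rule simulated exceeded 6%. The error risk is a choice made after seeing the data, at about 7-9%. Nor is a loss of power established. If the rank test replaces the ANCOVA and change is ranked, the loss is about 0-1 point for an item away from the floor and about 2-19 points for a single item near it, with a possible gain under skewed or heavy-tailed errors. These figures illustrate assumed means, SDs, correlations and a numeric trigger. They also take 40 per arm, although the efficacy set keeps only participants with all four infusions. Confidence is high in the textual gaps and limited in the sizes.

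For Weeks 14 and 20, under Table 1 the contrasts, paired tests and Cohen's d would have no scheduled data. It would be wrong to conclude that the primary result is compromised: the Week 26 ANCOVA does not use those visits.

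**What to change.** **Fallback**

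- State in SAP 5.1.1 and in both model sections of 5.2.2 that the ANCOVA adjusted for baseline and the three strata, and likewise the repeated-measures model, remains the analysis of record whatever the diagnostics show.
- Replace Mann-Whitney in 5.2.2, and the open nonparametric clause in 5.1.1 as it applies to these models, with a prespecified rank ANCOVA: rank of the Week 26 score on rank of baseline plus the three strata. Report it as a sensitivity analysis in every case.
- Delete the clause that permits unspecified data-driven adjustments, or limit it to named sensitivity analyses.
- Align the baseline-only ANCOVA of 5.1.1 with the strata-adjusted model of 5.2.2.

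**Visits**

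- Reconcile the Investigational Plan, Table 1 and the Visit 6 and 7 procedures in the protocol.
- Unless scores are collected at those visits, limit the repeated-measures contrasts, paired tests and Cohen's d to Weeks 2, 6, 10 and 26, and to Weeks 10 and 26 for SF-36.

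**Cost.** SAP wording, slight extra programming and a protocol clarification; no new patients. The downside is that a primary ANCOVA has less power than a rank analysis if residuals are strongly skewed or heavy-tailed. Rank ANCOVA was 6-19 points higher in the unbounded cases simulated, but within 3 points of ANCOVA in all bounded VAS cases.
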